## 6.2 Inulin in animal models

Animal models show protective effects of inulin or similar compounds, which appear to be mediated by an increase in SCFA producers. Importantly, these studies demonstrate that inulin is likely to be effective even when given concurrently with antibiotics. Animal models include cecal ligation and puncture (CLP), lipopolysaccharide (LPS) injection, challenge with *Citrobacter rodentium* or pathogenic *Escherichia coli* strains, and *Salmonella typhimurium* challenge with or without antibiotics. All models have their strengths and weaknesses, so it is remarkable that results align well across them. Inulin and similar fructo-oligosaccharides (FOS) seem to confer protective effects through multiple mechanisms all of which likely depend on SCFA fermenters. First, they maintain the protective colonic mucus layer. Inulin fermenters activate carbohydrate metabolism pathways and switch fuel utilization from dietary fiber to colonic mucus when inulin-like fibers are unavailable, causing thinning of the colonic mucus layer. Second, the bacteria nourished by inulin have direct antagonistic effects on pathogens by making protonated SCFAs which diffuse across Gram negative cell walls to delay pathogen growth. Luminal acidification by SCFAs also drives broad microbiome shifts towards relatively pH-tolerant, Gram positive obligate anaerobes. Third, SCFA producers induce host immunity. When SCFA-producing anaerobe levels increase during sepsis, there is induction of T regulatory cells (Tregs), reduction in activated dendritic cells, and downstream decreased DNA binding of NF- $\kappa$ B for an overall reduction in pro-inflammatory cytokines and reduced T cell anergy. In these animal studies, the protective effect is large, with dramatic differences in outcomes including weight loss, colitis severity, and mortality.

### 6.3. Inulin in the ambulatory setting

Inulin has been studied in over 400 ambulatory patients where it has shown excellent safety and tolerability. No serious adverse events have been reported in trials using doses up to 34 g/day inulin or 55 g/day mixed fiber, with self-resolving bloating the main side effect. Three trials specifically examined outcomes related to the ability of inulin to prevent colonization or infection. First, Dewulf *et al.* randomized 30 patients to inulin 16 g/day vs placebo; the inulin group had a doubling of *F. prausnitzii* and other SCFA-producers and concurrent decreases in serum CRP and LPS concentration. Second, Lecerf *et al.* randomized 60 volunteers 1:1:1 to placebo, a combination xylo-oligosaccharide (XOS), or inulin-XOS. The inulin group had the highest post-treatment SCFA levels and butyrate levels, the lowest circulating LPS, and decreased gene expression for the pro-inflammatory cytokines IL-1 $\beta$ , TNF $\alpha$ , and IL-12. Third, Miguez *et al.* found that an inulin-like fructo-oligosaccharides (FOS) preserved gut microbiome diversity after broad-spectrum antibiotics, mitigated loss of SCFA producers, and increased butyrate levels 3-fold. **Table 1** lists selected studies of inulin in the ambulatory setting, focusing on those with results most relevant to this project.

[figure not shown]
**Table 1. Selected ambulatory trials testing inulin alone or in combination**

Author	Subjects	Intervention	Effect	AEs
Kruse 	8 healthy volunteers	Inulin 34 g/day	Increased Bifidobacteria , unchanged SCFA levels	Self-resolving bloating and flatulence.
Dewulf 	30 obese women	inulin 16 g/day (50% FOS enriched) x 3 months	Increased Bifidobacteria and F. prausnitzii and decreased LPS.	Self-resolving bloating and flatulence.
Lecerf 	60 healthy volunteers	inulin 3g/day plus 1g/day XOS	Increased fecal SCFAs, decreased LPS, attenuated LPS-induced serum changes in IL-1b and IL-13.	Self-resolving bloating and flatulence, small decrease in general well-being.
Azpiroz 	36 with IBS	inulin 8g/day x 4 weeks	Increased Bifidobacteria .	None reported.
Canfora 	44 obese pre-diabetic adults	inulin 15g/day x 12 weeks	Increased Bifidobacteria .	None reported.
Garcia-Peris 	31 adult women with gynecological cancer	inulin 12g/day x 4 weeks (50% FOS enriched)	Increased in Lactobacillus and Bifidobacteria .	Self-resolving bloating.
Holscher 	29 healthy adults	inulin 7.5g/day x 21 days (agave-derived)	Increased Bifidobacteria .	None reported.
Petry 	32 obese female adults	inulin 20 g/day x 4 weeks	Increased Bifidobacteria .	None reported.
Rahat-Rozenbloom 	25 healthy obese or lean adults	inulin 24 g/day x 3 days	Increased serum SCFAs.	None reported.
Ramirez-Farias 	12 healthy adults	inulin 10g/day x 16 days	Increased Bifidobacteria and F. prausnitzii , no change in fecal SCFAs.	None reported.
Vandeputte 	42 healthy adults	inulin 12g/day x 4 weeks	Increased Bifidobacteria .	None reported.

### 6.4 Inulin-like fibers in the ICU

Inulin has not been studied in the ICU but data can be extrapolated from ICU trials of similar fructo-oligosaccharides (FOS). To date, there are no reports of serious adverse effects or major intolerance with over 1,000 patients studied. Doses have been used up to 36 g/day for 5 weeks. This emerging safety data is robust enough that consideration of supplemental fiber has

been incorporated into relevant ICU nutrition guidelines. Data on the effects of inulin-like FOS on infections in the ICU is scarce but promising. Three double-blind, randomized ICU trials tested a commercial synbiotic containing *Lactobacillus spp.* and mixed soluble prebiotic fiber including some inulin (up to 20 g/day total). In these studies, the overall rates of ICU-acquired infections were 16-27% lower in the group receiving prebiotic fiber, although MDR infections were not separately examined. In an open-label trial of mixed fiber up to 24 g/day in 30 critically ill adults, the median hospital length of stay was 5 days shorter in the fiber group and the overall rate of complications, including feeding-related complications was lower. This provides important reassurance given the concerns occasionally raised regarding prebiotics in patients with altered small bowel or colonic motility. **Table 2** lists selected studies of fiber supplementation in the ICU, focusing on those with results most relevant to this project

**Table 2.** Selected ICU-based trials testing inulin or similar fibers, ordered by decreasing amounts of fiber.

Author	Subjects	Intervention	Effect	AEs
O’Keefe 	13 ICU patients (most with pancreatitis)	32 g/day wheat dextrin up to 5 weeks	Higher fecal SCFA producers and SCFAs.	None reported.
Karakan 	30 ICU patients with pancreatitis	24 g/day mixed soluble and insoluble fiber (open label)	Shorter hospital stays and lower complications.	Self-resolving bloating.
Knight 	259 ICU patients on ventilation	20 g/day mixed fiber synbiotic including 5 g/day inulin	Trend towards lower rates of VAP.	None reported.
Kotzampassi 	65 ICU patients with SIRS	20 g/day mixed fiber synbiotic including 5 g/day inulin	Fewer infections and less diarrhea.	None reported.
Majid 	22 adults in the ICU	inulin 7g/day	No difference in Bifidobacteria and lower F. prausnitzii .	None reported.
Spapen 	25 ICU patients with septic shock	22 g/L guar fiber enteral feeding, dose individualized	Less diarrhea.	None reported.
Spindler-Vesel 	113 ICU trauma patients	17 g/day average mixed soluble fiber-synbiotic	Fewer infections.	Higher gastric residuals.

### 6.5 Summary of previous experience with inulin

Our prospective ICU cohort data provides real-world data supporting the hypothesis that inulin, by nourishing SCFA producers, will lead to decreased pathogen colonization and infection in the ICU. Animal studies show that inulin confers protection across various pathogen challenge models and sepsis models including LPS injection and cecal ligation-and-puncture. Ambulatory studies of inulin demonstrate safety and generally show increases in SCFA producers related to inulin. Few ICU studies have tested inulin, but there is ample ICU experience with inulin-like fibers that provides reassurance that high doses of fiber are safe even in the context of sepsis and hypotension in the ICU.

### 7. Study objectives

[figure not shown]
The short-term goal of the study is to test inulin for the prevention of MDRO colonization and infection in the intensive care unit. The long-term goal of this research is to develop antibiotic-free strategies that prevent or ameliorate ICU-acquired infections.

## 8. Study Design

This will be a double-blind, randomized, placebo-controlled trial with two doses.

## 9. Intervention

Block randomization (blocks of six) will be performed with 1:1:1 random computer allocation of subjects into the three study arms. In the two inulin arms, chicory root-derived inulin (Cargill Inc., Wayzata, MN) will be diluted in 250 ml of sterile water and given at 8 or 16 g twice daily (**Figure 4**). The placebo arm will receive the same volume of sterile water twice daily, with the intervention given for 7 days or until death or hospital discharge. Prior studies suggest that these doses are likely to be safe and sufficient to confer benefit, even in the setting of critical illness. Subjects, investigators, and the treating ICU team will be blinded to the intervention arm, with blinding managed by the CUMC Research Pharmacy which will provide labeled, de-identified, semi-opaque fluid bags containing inulin/placebo in accordance with the U.S. Code of Federal Regulations governing labelling of new investigational drugs (21CFR 312.6). The intervention will be taken orally or given with enteric feeding by nursing staff overseen by the study team, with the first dose administered within 6 hours of ICU admission. The time course for the intervention and remaining study assessments is shown below in **Table 3**.

**Figure 4.** Chemical structure of inulin. Inulin is a naturally occurring polysaccharide derived from chicory root, agave, garlic, and other vegetable sources; it is a long chain carbohydrate of fructose polymers with  $\beta(1,2)$  glycosidic linkages which are indigestible by human enzymes but fermented by colonic anaerobic bacteria into short-chain fatty acids (chemical formula:  $C_{6n}H_{10n+2}O_{5n+1}$ ).

**Table 3.** Time course of intervention and main assessments during the study.

Type of Assessment	Inulin----->			Monitoring----->			
	Day 0	Day 3	Day 7	Day 14	Day 30	3 months	6 months
Rectal swab	X	X	X	X	X		
Whole stool	X	X	X	X	X		
Clinical data	X	X	X	X	X	X	X
Telephone follow-up						X	X

### 9.1. Storage, accountability, and dispensing

The study medication will be delivered to the CUMC Research Pharmacy as a powder via Swanson/Cargill protected from moisture and light and accessible only to authorized individuals. The medication will be stored at 20-25°C in powder form and reconstituted before dispensation. Medication labels will be blinded. The Research Pharmacy will maintain a record of the inventory and disposition of all medication and placebo. This receipt record will include from whom the medication was received, to whom it was distributed, the date, quantity, and lot number. The study medication has the following characteristics (**Table 4**).

**Table 4:** Study medication characteristics.

Product name:	Inulin powder
Manufacturer:	Cargill Inc., [name]
Distributor:	Swanson Health, [name]
Appearance:	White powder
Flavor:	Neutral to sweet
Bulk density:	0.6 g/mL
Solubility:	>100 g/L
Moisture:	3.41%
Dry stability:	4 years

## 9.2. Rationale for the selection of duration and dose.

9.2.1. Rationale for duration. Inulin will be given for 7 days with the primary outcomes adjudicated after 3 days. The Day 7 data will be used to test whether an effect can be extended or whether a delayed effect is present. In our cohort data, 84/126 (67%) new infections occurred within 3 days and 97/126 (77%) within 7 days. This shows that any ICU-based intervention seeking to prevent infections must work quickly if it is to be effective. Meanwhile, our preliminary cohort data suggests that fiber can have an impact even within this short timeframe (Figure 3). A final assessment will be made on the day of hospital discharge in subjects who are to be discharged prior to Day 14.

9.2.2. Rationale for dose. In the ambulatory setting, inulin impacts SCFA producer levels at doses of 12 to 16 g/day, with biologic effects relevant for ICU patients (e.g., decreases in serum LPS and CRP). Approximately 16 g/day therefore represents the minimum dose at which an effect *might* be seen; this was selected for the low dose arm of the study. However, patients in these ambulatory studies were not critically ill and did not receive antibiotics. It is possible that inulin will have lesser effects in the ICU compared to the ambulatory setting, and logical to test higher doses. To select a maximum study dose, we referenced our own experience with dietary fiber in the prospective cohort and published tolerability data from ICU studies of inulin-like prebiotic fiber. In our prospective ICU cohort, 30 g/day was the maximum observed dose of dietary fiber, and was not associated with any intolerance. In published literature, O’Keefe *et al.* reported tolerance up to a maximum of 36 g/day wheat dextran in the ICU. We therefore selected 32 g/day for the high dose study arm because it lies between these values and is exactly double a dose with proven biologic activity.

## 9.3. Regulatory

No subjects will be enrolled until after review and approval by the U.S. Army Medical Research and Materiel Command (USAMRMC) Office of Research Protections (ORP), Human Research Protection Office (HRPO). The PI holds FDA IND [REDACTED] (FDA date: September 4, 2018) for inulin for the prevention of MDRO colonization/infection in the ICU or other at-risk settings. Safety and adverse effects will be overseen by the PI in conjunction with [name], the Director of Medical Intensive Care Units at our institution, who will serve as the Data Safety Monitoring Officer (DSMO) and will convene an appropriate Data Safety Monitoring Board (DSMB) for the study. Before initiating research, the study will be registered on clinicaltrials.gov.

## 9.4. Documentation of administration of the intervention

The study team will work with the treating ICU team to ensure that the study drug is delivered in a timely manner. The time and dose of each medication administration will be documented at each study assessment by referring to the documentation of medication administration within the

electronic medical record (EMR). Patients will be enrolled with a goal of administering the intervention within 24 hours of ICU admission and it will be considered a protocol deviation if the intervention is administered more than 48 hours from ICU admission.

## 10. Outcomes

Primary and secondary outcomes focus on the comparison of baseline to Day 3 samples. This project will also gather samples at ICU Days 7, 14, and 30. These additional samples will be used to construct longitudinal time series data and test for differences between groups that may be slower to emerge (e.g., baseline vs Day 7 comparisons).

10.1. Primary outcome: Relative abundance of SCFA producers through ICU Day 3. The within-individual change in the relative abundance of SCFA producers will be determined by 16S rRNA gene sequencing of rectal swabs and compared between intervention groups. From extracted rectal swab DNA, polymerase chain reaction (PCR) will be performed on a Bio-Rad T100 Thermal Cycler (Bio-Rad, Hercules, CA) to amplify the V4 hypervariable region of the 16S ribosomal RNA gene with primers derived from Klindworth *et al.* appended with overhang sequences for compatibility with Illumina index and sequencing adapters (Illumina, San Diego, CA). The relative abundance of SCFA producers levels will be determined as the sum total across the bacterial species known to ferment the SCFA butyrate and subtracted within each individual to obtain the change (Day 3 minus baseline).

10.2. Secondary outcome: MDRO colonization status on ICU Day 3. MDRO colonization status will be based on Day 3 rectal swab cultures, classified categorically and compared between intervention groups. MDROs will be defined as methicillin-resistant *Staphylococcus aureus* (MRSA), vancomycin-resistant *Enterococcus* (VRE), and MDR Gram negative bacteria (defined as Gram negatives with *in vitro* non-susceptibility for third-generation cephalosporins). Based on culture results, Day 3 MDRO colonization status will be classified categorically and compared between groups.

### 10.3. Additional outcomes:

10.3.1. *Feasibility.* Descriptive demographic and clinical data will be compared across study groups to assess adequacy of randomization. Summary statistics (count data) will be recorded for patients across all 3 intervention arms to assess feasibility as (1) the enrollment rate (enrolled)/(enrolled+refusals) over each 12 month period; (2) protocol adherence (proportion of randomized subjects who receive 1 or more doses of the allocated intervention); and (3) fidelity of the intervention (defined as the proportion of high/low inulin allocated vs received and also categorically as receipt of 90% or more allocated doses of inulin across groups). Feasibility goals are as stated in Aim 1.

10.3.2. *Rates of pre-specified AEs.* There will be active ascertainment of AEs in the following categories, which will be compared between intervention groups. This will be done through the end of the intervention period (ICU Day 7) and also through Day 30/discharge to assess for delayed AEs.

- Stool frequency, measured by subject or nursing report by the number of spontaneous stools over the 24 hours preceding each assessment;
- Stool consistency, measured by subject or nursing report as an ordinal variable (0-4) over the 24 hours preceding each assessment;

- Abdominal bloating, measured by subject or nursing report as an ordinal variable (0-3) over the 24 hours preceding each assessment.
- Electrolyte abnormalities, measured by examining for differences in median values, minimum/maximum values, and proportions of values outside the normal range. This will be done for glucose, calcium, magnesium, phosphate, potassium, and sodium.
- Nausea, vomiting, obstruction, and abdominal pain. These will be recorded as present or absent based on bedside assessment of the subject or based on the nursing impression.
- Culture-proven infections, which will be considered both an AE and an outcome (see 10.3.4).

10.3.3. *Antibiotic resistance gene fraction on ICU Day 3.* DNA will be extracted from rectal swabs (MoBio PowerFecal, Carlsbad, CA) and assessed using multiplex quantitative PCR (Qiagen Cat. No. 330261, Valencia, CA) for 87 common antibiotic resistance genes. Within-individual differences in multiplex qPCR results will be compared from baseline to Day 3 both as summed changes and within relevant gene categories (e.g.,  $\beta$ -lactamase resistance genes) and compared between intervention groups.

10.3.4. *Culture-proven MDR infections through ICU Day 30.* Antibiotic-resistant infections will be defined as those showing all of the following: (1) site-specific symptoms or signs of infection, (2) initiation of targeted antimicrobials by the treating ICU team, and (3) molecular diagnostics or cultures showing an MDRO as adapted from the CDC and NHSN and previously used by our group (**Table 4**). Rates of infections will be compared between intervention groups as a sum total, and separately for 3 distinct periods: the intervention period of Day 0 to 7, the Day 7 to 30 period, and the Day 30 to 6 month period.

**Table 4. Criteria used to adjudicate culture-proven MDR infections for.** Criteria based on CDC/NHSN guidelines.

Criteria	Operationalization	Example
1. Site-specific symptoms or signs of infection.	
 
• Pulmonary: documentation of new or worsening cough or imaging consistent with an infection
 
• Urinary: fever, dysuria, increased urinary frequency, flank pain, mental status changes, or hypotension and clinical exclusion of other causes for infection.
 
• Bloodstream: clinical evidence of a bloodstream infection (fever, chills, or hypotension) without alternative sources for infection
 
• Stool: documentation of new loose stools or frequent stools <math>\geq 3</math> per 24 hours
 
• Wound: appropriate surgical site incision or wound with discharge, warmth, or erythema.
 
	Cough and a chest X-ray showing new infiltrate.
2. Positive cultures or other diagnostics with an MDRO.	
 
• Pulmonary: quantitative or semi-quantitative sputum or bronchoscopic cultures
 
• Urinary: <math>\geq 10^5</math> CFU/mL growth.
 
• Bloodstream: growth of a recognized bloodstream pathogen from blood but not another site or growth of a NHSN commensal from blood but not another site.
 
	Sputum culture growing $>10^5$ CFU/ml of K. pneumoniae resistant to ceftriaxone.

- Stool: positive PCR for the *C. difficile* toxin B gene (Cepheid or BioFire) or positive toxin B EIA
- Wound: growth of aseptically obtained organisms.

3. Initiation of targeted antibiotics within 24 hours.	Antibiotics showing non-susceptibility using standard CLSI breakpoints or appropriate empiric antibiotics initiated at the time of clinical suspicion/testing and continued for $\geq 3$ days or initiated within 24 hours following the availability of diagnostic testing showing a culture-proven infection.	Initiation of ceftriaxone when the X-ray was ordered; later changed to meropenem.
---	--	---

10.3.5. *Fecal SCFA levels.* The SCFAs butyrate, acetate, and propionate will be measured from whole stools on a 6490 triple quadrupole mass spectrometer and compared between intervention groups using the first stool sample produced after the Day 3 assessment. Patients who fail to produce a stool from Day 3 to 7 will be excluded from this analysis.

10.3.6. *Proportion of goal calories through ICU Days 3 and 7.* Proportion of goal calories consumed will be defined by manually extracting data from electronic nursing flow sheets. Intake during the intervention be calculated by multiplying enteral or oral feeding caloric content by the flow rate or percentage of meal consumption. A patient-specific calorie target will be calculated by a registered clinical dietician using the Mifflin-St. Jeor equation and the Penn State 2003b and 2010 equations, taking into consideration age, body mass index, ventilation status, and comorbidities. The proportion of goal calories consumed will then be calculated as observed nutritional intake divided by calorie target. Day 3 and Day 7 proportions will be compared between intervention groups.

10.3.7. *Length of ICU stay.* Length of ICU stay through Day 30 will be compared between treatment groups, with Fine and Grey methods used to adjust for death as a competing risk. Length of ICU stay will be measured from the first to the last set of recorded ICU vital signs.

10.3.8. *Length of hospital stay.* Similarly, length of hospital stay through Day 30 will be compared between treatment groups, again adjusting for death as a competing risk. Length of hospital stay will be measured from the first set of recorded ICU vital signs to the last set of hospital recorded vital signs.

10.3.9. *Mortality through ICU Day 90.* Death data will be extracted from the hospital EMR which immediately captures in-hospital death and receives monthly mortality updates from the National social security death index. Kaplan-Meier methods will be used to compared 30- and 90-day mortality between treatment groups.

10.3.10. *Self-assessed quality of life at 6 months.* Subjects or their caregivers will complete the EQ-5D-5L and Katz ADL questionnaires to test their quality of life at 3- and 6 months post ICU admission. Composite data will be compared between intervention groups.

10.3.11. *Time series data including Day 7 outcomes.* Time series data will be built and visualized for all relevant outcomes. We will explore the possibility of a delayed effect by testing for differences between groups from baseline to Day 7. If there is an observed effect, the Day 14 and Day 30 data will allow us to assess its durability.

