#### **15. Safety and adverse events (AEs)**

Adverse health events, laboratory irregularities, and even death are expected in ICU patients with sepsis and it would be difficult or impossible to accurately document and label all adverse health events. This is a common problem faced by ICU trials. The solution recommended by academic critical care research groups (e.g., Cook *et al.*) is to pre-specify AEs of interest for careful monitoring. In keeping with this approach, this study will produce detailed reports of these AEs for the DSMC at standard intervals while only unanticipated problems that also meet criteria for serious adverse events (SAEs) will be reported to the DSMC in real time. AEs will be reported for all individuals who have received one or more doses of the intervention. This study has pre-specified AEs in the following categories.

- Bloating: graded 0-3 based on patient report: patient mean and maximum values will be reported;
- Stool consistency and frequency: graded 0-4 for consistency and with an integer denoting frequency over 24 hours based on nursing report. For each patient, mean and maximum values will be reported;
- Electrolyte imbalances: For each patient, the minimum and maximum values for serum calcium, magnesium, phosphate, potassium, and sodium will be reported. This will be done for the 7 days of the intervention period and separately from Day 7 through Day 30/discharge;
- Gastrointestinal AEs: the gastrointestinal AEs of nausea, vomiting, bowel obstruction, and abdominal pain will be recorded as present or absent for each assessment and separated from other AEs to improve early pattern recognition by the DSMO;
- Infections: Infections are both an AE and an outcome and will be adjudicated as previously described. For each infection, the date of the infection, suspected site, organism, and antibiotics received will be recorded. Infections will be further classified as MDR vs non-MDR using the criteria previously described;
- Death: death will be gathered from the hospital EMR, which interfaces with the social security death index.

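### The delayed-AE comparison has no start day and, read plainly, contains the on-treatment events; bloating, stool and GI symptoms have no separate post-Day-7 comparison

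*Combined protocol and SAP*

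**What the plan says.** Section 10.3.2 lists six groups of pre-specified AEs: stool frequency, stool consistency, bloating, electrolytes, the present/absent symptoms (nausea, vomiting, obstruction, abdominal pain) and culture-proven infections. On timing, it has the groups compared up to ICU Day 7, when dosing ends, and "also through Day 30/discharge to assess for delayed AEs".

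Elsewhere the timing differs by category:

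- **Electrolytes (section 15).** Two non-overlapping windows: "This will be done for the 7 days of the intervention period and separately from Day 7 through Day 30/discharge". Glucose is in the 10.3.2 list but not in this one.
- **Bloating (section 15).** "graded 0-3 based on patient report: patient mean and maximum values will be reported", with no period named.
- **Stool consistency and frequency (section 15).** "For each patient, mean and maximum values will be reported", again with no period.
- **GI symptoms (section 15).** These "will be recorded as present or absent for each assessment", with no split at Day 7.
- **Infections.** 10.3.2 refers to 10.3.4, which compares MDR infection rates in total and separately for Day 0 to 7, Day 7 to 30 and Day 30 to 6 months. Section 15 records a date for every infection but states no window for non-MDR infections.

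Bedside assessments are at baseline and Days 3, 7, 14 and 30, ending at discharge or death (section 13). Bloating, stool and symptom items refer to the 24 hours before each assessment (10.3.2 and 13.3.1).

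**The concern.** Dosing lasts 7 days, so a delayed AE is naturally one that arises after Day 7. The comparison named for finding such events shares its wording with the Day 7 comparison and only moves the end date. On that reading every on-treatment event is counted again in the delayed result.

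Two errors follow. An excess confined to the dosing week can appear as delayed harm. A true excess after dosing can be masked by early events common to all arms. The section 15 maximum has the same weakness: with no period attached, it does not show whether a patient's worst score came during dosing or after it.

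The categories left without a split include bloating and distension, which section 11.3 names as the most common side effects of inulin. Section 5.2 makes safety part of the trial's purpose. If the window is chosen only after the data are unblinded, any statement about delayed harm is post hoc.

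**Working it through.** **1. The plan's own timing figure.** Section 9.2.1 gives cohort infections within 3 and 7 days: 84/126 = 66.7% and 97/126 = 77.0%, matching the stated 67% and 77%. The remainder is 126 − 97 = 29, and 29/126 = 23.0%. If AEs were timed like those infections, about 77% of a count through Day 30 would be on-treatment. Infections are not GI symptoms, so this is only indicative.

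**2. Which categories have a separate post-Day-7 comparison?**

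| Category | Separate window stated? |
|---|---|
| Electrolytes | Yes, section 15 (glucose not listed there) |
| MDR infections | Yes, 10.3.4 |
| Non-MDR infections | Not clearly |
| Stool frequency and consistency | No |
| Bloating | No |
| Nausea, vomiting, obstruction, abdominal pain | No |

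**3. Illustration, present/absent symptoms only.** From the plan: 30 per arm (17.3), inulin arms combined to give 60 v 30, two-sided 0.05 (17.1). Assumed: all AE rates, independence of early and late events, everyone observed to Day 30, and Fisher's exact test. Rejection rates come from exact enumeration.

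Cumulative rate = 1 − (1 − on-treatment rate)(1 − later rate).

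*Scenario A: early excess, nothing delayed.* On treatment 40% v 10%; afterwards 10% v 10%.
- Inulin: 1 − 0.60 × 0.90 = 0.46. Placebo: 1 − 0.90 × 0.90 = 0.19.
- Cumulative test significant: 69%.
- Separate post-Day-7 test significant: 3%.
- Planned Day 7 test (40% v 10%) significant: 87%.

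*Scenario B: delayed excess behind common early events.* On treatment 40% in both; afterwards 25% v 5%.
- Inulin: 1 − 0.60 × 0.75 = 0.55. Placebo: 1 − 0.60 × 0.95 = 0.43.
- Power, cumulative: 17%.
- Power, separate: 65%.

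*Scenario B, separate window, with fewer patients left after Day 7* (retention assumed):

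| Remaining, inulin v placebo | Power |
|---|---|
| 60 v 30 | 65% |
| 40 v 20 | 46% |
| 30 v 15 | 26% |
| 20 v 10 | 7% |

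**4. Other assumed rates.** A two-proportion power formula (60 v 30, two-sided 0.05) shows the same pattern. With delayed rates of 35% inulin v 10% placebo, the separate window has about 75% power. The cumulative comparison has about 57, 44, 34, 27 and 22% when the shared early rate is 10, 20, 30, 40 and 50%. With 10% later in both groups, early rates of 40% v 20% (cumulative 46% v 28%) give a false delayed signal about 37% of the time, and 50% v 20% (cumulative 55% v 28%) about 69%.

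**The case against.** The strongest reply is that this is unclear wording in one additional outcome, and much of that stands.

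- **No start day is stated.** A reader might infer that the plan prescribes Day 0 to Day 30 counts. It does not. Cumulative is the plain reading, but it is an inference, and where the plan spells out windows they are separate.
- **Electrolytes are not the only split category.** A reader of section 15 alone might think so, but 10.3.4 splits MDR infections too.
- **Section 15 does not say that bloating and stool scores cover the whole follow-up.** It names no period.
- **A binary model fits only the present/absent symptoms.** Bloating and stool consistency are ordinal and stool frequency is an integer, so the percentages above do not carry over to them.
- **The data are separable.** Items are recorded at each assessment, and 10.3.11 plans time series for relevant outcomes. Nothing is lost at collection.
- **In scenario A the Day 7 comparison would usually expose the early excess.** It is itself significant in about 87% of trials and would be reported alongside.
- **The separate window pays for discharge and death.** The cumulative comparison keeps early leavers; the separate one loses them and conditions on a post-randomisation subset still in hospital. At 20 v 10 its 7% power in scenario B is below the cumulative 17%.

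What the reply does not remove is that, for bloating, stool and GI symptoms, no post-Day-7 group comparison is specified, and the one offered for delayed AEs does not isolate them. Separable data and planned plots do not fix which comparison will be made.

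**Conclusion.** The point holds as a gap in the analysis wording. As plainly read, the 10.3.2 comparison cannot distinguish delayed from on-treatment AEs. The gap covers stool frequency, stool consistency, bloating and the present/absent GI symptoms, with non-MDR infections unclear. It does not cover electrolytes with a section 15 window or MDR infections.

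The 69% v 3% and 17% v 65% contrasts show that the choice of window can matter. They rest on assumed rates, independence and complete observation, and the benefit of the separate window shrinks as patients leave.

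A reader might infer that the trial's safety monitoring is compromised. The documents do not support that: interim stopping in 17.4 rests on toxicity and toxic-death boundaries, not on this comparison. Nor does any sample size, or any primary or secondary result, depend on it. Severity is minor.

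**What to change.** In 10.3.2, define the delayed period as after Day 7 to Day 30/discharge. There and in section 15, extend the convention already used for electrolytes and in 10.3.4 to the remaining AE categories, including non-MDR infections and glucose:

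1. Compare each category through Day 7 and, separately, after Day 7 to Day 30/discharge.
2. For stool frequency, stool consistency and bloating, base the second comparison on the Day 14 and Day 30 assessments, and state the period for each mean and maximum.
3. Report the number assessed per arm in each window.
4. Keep the through-Day-30 table as description.

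The cost is a few lines of text and one extra table, with no new data. The downside is that the later comparison covers only patients still in hospital, a post-randomisation subset with limited power. The plan should say it will be read as descriptive safety information, and that a non-significant result there is not evidence that delayed harm is absent.
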